3.1.4.1 Complete Response

Complete response (CR) is defined as all target organs (skin, liver, upper GI tract, and lower GI tract) evaluated as MAGIC aGVHD Stage 0 (see Section 4.5.6). For a response to be evaluated as CR, the patient must be in CR on the study day that response is evaluated and have had no intervening additional line of aGVHD therapy (as defined in Section 3.1.4.10).

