Appendix 6: Primary Disease Relapse or Progression Guidance

For multiple myeloma, relapse or progression is defined as meeting any one or more of the following criteria:

• Direct indicators of increasing disease and/or end-organ dysfunction (i.e., hypercalcemia, renal failure, anemia, and bone disease) related to the underlying clonal plasma-cell proliferative disorder

> This criterion is not used in calculation of time to progression or progression-free survival but can be reported optionally or for use in clinical practice

• Development of new soft tissue plasmacytomas or bone lesions (osteoporotic fractures do not constitute progression)

Definite increase in the size of existing plasmacytomas or bone lesions, defined as a 50% (and \geq to 1 cm) increase as measured serially by the sum of the product diameters of the measurable lesion.

- Hypercalcemia (> 11 mg/dL)
- Decrease in hemoglobin of ≥2 g/dL not related to therapy or other non-myeloma-related conditions
- Rise in serum creatinine by 2 mg/dL or more from the start of the therapy and attributable to myeloma
- Hyperviscosity related to serum paraprotein

For the purposes of assessing relapse free survival, if patient is in complete response (CR; as defined in Section 3.1.4.1), relapse is defined as meeting any one or more of the following criteria:

- Reappearance of serum or urine M-protein by immunofixation or electrophoresis
- Development of \geq 5% plasma cells in the bone marrow
- Appearance of any other sign of progression (i.e., new plasmacytoma, lytic bone lesion, or hypercalcemia; see above).

For myeloproliferative neoplasms, relapse from CR is defined as meeting one or more of the following criteria:

- Reappearance of bone-marrow disease, including blasts, monocytic blast equivalents, or fibrosis
- New extramedullary disease, including new or reappearance of splenomegaly, hepatomegaly, skin lesions, etc.

Institution of any therapy to treat persistent, progressive or relapsed malignancy, including the withdrawal of immunosuppressive therapy or treatment of relapse with donor lymphocyte infusion, will be considered evidence of relapse/progression regardless of whether the criteria described above were met. The use of preemptive

GDC-8264—Genentech, Inc. 122/Protocol GA43861, Version 4 donor lymphocyte infusion is not considered as relapse. Relapse will also be considered to have occurred if the criteria described above were not met but the cause of death was attributed to relapse.

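### Appendix 6 makes two myeloma relapse criteria depend on complete response of aGVHD instead of remission of the myeloma

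*Combined protocol and SAP*

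**What the plan says.** Appendix 6 supplements the relapse definition in Section 3.1.4.7. Its myeloma block has two parts.

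The first part is unconditional: "For multiple myeloma, relapse or progression is defined as meeting any one or more of the following criteria". Its items are end-organ indicators, new or growing plasmacytomas or bone lesions, hypercalcaemia, a fall in haemoglobin, a rise in creatinine, and hyperviscosity.

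The second part limits itself at the outset to relapse-free survival and continues: "if patient is in complete response (CR; as defined in Section 3.1.4.1), relapse is defined as meeting any one or more" of three items. These are "Reappearance of serum or urine M-protein by immunofixation or electrophoresis", at least 5% "plasma cells in the bone marrow", and any other sign of progression.

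The section referred to reads: "Complete response (CR) is defined as all target organs (skin, liver, upper GI tract, and lower GI tract) evaluated as MAGIC aGVHD Stage 0". On the day of evaluation the patient must be in that state and "have had no intervening additional line of aGVHD therapy".

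The myeloproliferative block comes next: "For myeloproliferative neoplasms, relapse from CR is defined as meeting one or more of the following criteria". It carries no section reference and no definition of CR.

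Two closing rules cover all diseases. Treatment started for the malignancy "will be considered evidence of relapse/progression regardless of whether the criteria described above were met", and a death attributed to relapse also counts as relapse.

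**The concern.** A criterion for return of the malignancy should depend on the state of the malignancy. Here it points, by explicit section number, to the response definition of a different disease process. Whoever programs the endpoint or builds the eCRF from this text would take the aGVHD response field, because CR has no other defined meaning in the protocol.

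Ascertainment of myeloma relapse would then depend on GVHD response, an outcome that may differ between the 35 mg and 75 mg cohorts. The study uses all available efficacy data to choose a dose, so a relapse count that moves with GVHD status could mislead even as a descriptive summary.

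**Working it through.** The plan states no figure on this point and no arithmetic applies. The check is to follow the reference and see which routes to a relapse depend on it.

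1. **Is there another definition of complete response?** No. Section 3.1.4.1 speaks only of skin, liver and the upper and lower GI tract. Section 3.1.4.7 names acute leukaemia, myelodysplastic syndrome, lymphoma and chronic lymphocytic leukaemia, but neither myeloma nor myeloproliferative neoplasms. Where Appendix 6 deals with chronic lymphocytic leukaemia it refers to complete remission before transplantation, which is a malignancy state.

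2. **Can the affected patients be enrolled?** Yes. Section 4.1.1 allows any indication for transplantation. Section 4.1.2 excludes persistent malignancy, so enrolled myeloma patients should largely be in remission, the group the second list appears meant for.

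3. **Which criteria really depend on the reference?** Two of the three. The third item, other signs of progression, repeats findings on the unconditional list. M-protein reappearance and the plasma-cell threshold are not on that list.

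4. **Literal result for a myeloma patient in remission**, taking CR status on the day of the finding and setting aside the restriction to relapse-free survival:

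| Finding | All aGVHD organs Stage 0, no further line | Residual aGVHD, or a further line |
|---|---|---|
| M-protein reappears, nothing else | relapse | no relapse |
| Marrow plasma cells at least 5%, nothing else | relapse | no relapse |
| Any item on the unconditional list | relapse | relapse |
| One of the first two, then treatment for the malignancy | relapse at the finding | relapse, possibly dated later |
| One of the first two, then death attributed to relapse | relapse at the finding | relapse, possibly dated later |

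The later date follows from the dating rule in Appendix 6: the earliest of criteria met, malignant disease detected and treated, or death reported as relapse. If the first never occurs, one of the other two sets the date.

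5. **Which endpoints are reached?** Section 6.6.2 lists cumulative incidence of relapse and the failure-free survival rate, both exploratory. For failure-free survival the exposure is narrower. Section 3.1.4.12 already counts a further aGVHD line as failure, so only patients with residual aGVHD and no such line can be misclassified. A delayed date changes the value at a fixed time only if it moves the event past that time; those times are redacted.

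**The case against.** The strongest reply is that nobody would apply the rule this way. The appendix is guidance, the items concern M-protein and marrow, and a haematologist would read CR as remission of the myeloma. That is probably what was intended and would limit the harm in practice. It does not repair the text: the reference is an explicit section number, and Section 4.5.5 says endpoints are calculated programmatically.

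A second reply is that the sentence serves relapse-free survival only, which is not among the endpoints visible in the public copy (one exploratory bullet in Section 6.6.2 is blank). This is fair. Taken strictly, the two criteria would then feed no visible endpoint at all. The effect on relapse incidence and failure-free survival therefore assumes that the list is used for them. The reply does not remove the problem; it shows that correcting the reference alone is not enough.

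Third, the treatment and death rules recover many events. That stands, apart from the possible delay and apart from patients with an isolated finding who are neither treated for relapse nor die of it within follow-up.

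A reader might try to size the effect from Section 1.1.1, where the Day 28 response rate in high-risk patients is 44% (95% CI 38% to 50%), and infer that at least 1 - 0.44 = 56% are not in complete response. The documents do not support this as a measure of the problem. It is one time point in a historical corticosteroid cohort, whereas relapse is followed for about a year. It also counts patients without GVHD response, not misclassified relapses.

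**Conclusion.** The cross-reference is wrong as written. For two myeloma criteria it lets the same malignancy course be classified differently according to aGVHD status. The consequence is small and confined to exploratory, descriptively summarised endpoints. Misclassification needs a myeloma patient with an isolated M-protein or marrow finding, who at that moment has residual aGVHD or has had a further aGVHD line, and who has no other sign on the unconditional list. Relapse treatment or relapse death later turns a missed event into a possibly late one. The disease mix is not given, so the number cannot be computed and could be zero.

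Three stronger readings are tempting but not supported:

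- **Non-relapse mortality.** Section 3.1.4.8 defines it by attribution of the death, and no use of a relapse date for it is stated. No direct effect is shown.
- **Bias between doses.** If one dose cleared more aGVHD, the two criteria would be open to more of its patients, so the direction is conceivable. With approximately 20 patients per cohort and probably few with myeloma, no size can be claimed.
- **Myeloproliferative neoplasms.** That block uses the abbreviation without the section reference, and its items make sense only for remission of the neoplasm. The term is ambiguous because it has no definition of its own; dependence on aGVHD is not established.

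**What to change.** In Appendix 6:

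- In the myeloma block, replace the bracketed reference to Section 3.1.4.1 by complete remission of the multiple myeloma.
- In the same sentence, replace the restriction to relapse-free survival by the listed endpoints that the criteria serve: cumulative incidence of relapse and failure-free survival, plus any redacted endpoint that uses them.
- In the next block, write relapse from complete remission of the myeloproliferative neoplasm, so that CR keeps its single aGVHD meaning.
- Add one sentence stating that aGVHD response status plays no part in any relapse criterion.

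The Data Analysis Plan and eCRF wording should match. The cost is a few phrases. No new data are needed, and the sample size is unaffected.
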